Appendix F
Restricted and prohibited medications

PROHIBITED AND RESTRICTED MEDICATIONS

Asthma medication restrictions

Table 1 Asthma medication restrictions

Medication	Prohibited/restricted	Details
Maintenance asthma controller medications containing a LABA and/or LAMA	Restricted only on days of scheduled clinic visits	Usual ICS-LABA/LAMA should not be taken prior to scheduled spirometry and ECG assessments (to be administered once assessments are completed)
Short acting beta-agonists (SABA)	Restricted only on days of scheduled clinic visits	SABA should not be used within 6 hours prior to scheduled spirometry and ECG assessments.
Zileuton	Prohibited	Not allowed 30 days prior to Visit 1; during treatment period

Other medication restrictions

Table 2 Other medication restrictions

Medication	Prohibited/restricted	Details
Live Attenuated Vaccines	Prohibited	Not allowed 30 days prior to randomization; during treatment period, and 16 weeks after the Last Dose
Inactive/killed vaccinations (e.g. inactive influenza)	Restricted	Allowed provided they are not administered within within 1 week

		before/after any IP administration.
Any immunomodulators or Immunosuppressives except systemic steroids used: 1) for the treatment of asthma exacerbations and 2) as intra-articular injections	Prohibited	Not allowed within 3 months prior to the date informed consent is obtained; during treatment period; 3 Months or 5 Half Lives (whichever is longer) after Last Dose
Any immunomodulators or immunosuppressives – topical	Restricted	Topical administration of immunosuppressive medication may be allowed at the discretion of the Investigator after discussion with the AstraZeneca Study Physician
Blood products or immunoglobulin therapy	Prohibited	Not allowed 30 days prior to date of ICF; during treatment period
Any marketed (eg omalizumab) or investigational biologic treatment	Prohibited	Not allowed 4 months or 5 half-lives (whichever is longer) prior to Visit 1; during treatment period; 4 months or 5 half-lives (whichever is longer) after the last dose of the investigational product
Other investigational Products (including investigational use of an approved drug)	Prohibited	Not allowed 30 Days or 5 Half Lives (whichever is longer) prior to Visit 1; during treatment period
Allergen Immunotherapy	Restricted	Allowed if on stable therapy, or stable seasonal therapy,

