| SC | Subcutaneous |
| SD | Standard deviation |
| SI | Standard International |
| SOC | System organ class |
| TBL | Total bilirubin |
| TBNK | T cell, B cell and Natural Killer cell |
| ULN | Upper limit of normal |
| WBDC | Web-based data capture |
| WPAI+CIQ | Work Productivity and Activity Impairment Questionnaire plus Classroom Impairment Questions |

AMENDMENT HISTORY

| Date | Brief description of change |
|---------------|--|
| 14 March 2017 | 
• Remove the redundant descriptions in Study design section• Full analysis population is to be used for all non-PK parameters• Further clarification of baseline selection• Remove the redundant item on the list of protocol deviation• Exacerbation rate is to be calculated separately for on-treatment period, and post-treatment period to investigate whether the underlying exacerbation rate changes with withdrawal of treatment• Annual rate of health care encounters is to be calculated separately for on-treatment period, and post-treatment period to evaluate whether the underlying health care encounters change with withdrawal of treatment• Adverse events occurrence period definitions for on-treatment, post treatment, and on-study periods, are further clarified• Drug Dictionary is updated to WHODRUG• Addition of Japanese interim analyses to facilitate regulatory reporting requirements in Japan• Clarify the analyses for the clinical study report will follow two phases including Adult Completion Analysis and Adolescent Completion Analysis• Adjustment of analysis visit window according to collection schedule according to the rules specified in final pivotal studies' analysis• ADA analyses are expanded according to global ADA analysis plan and the nature of study design |

11 December
2017

Amended to reflect the following updates (minor updates are not listed):

- Add Double-blinded to the study title to be consistent with the final protocol amendment
 - Drug Dictionary is updated to AZDRUG due to the timeline change in drug dictionary migration
 - Add the rationale to remove data from SIROCCO centre (centre in BORA) in summary
 - Define anomalies in the plasma concentrations and clarify how these patients will be reported
 - Clarify the baseline definition, especially for pre-/post-BD FEV1
 - Update the AE on-treatment period for analysis of adolescent data during the adult completion analysis

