2.2.1 Important protocol deviations

The important protocol deviations are important in that they may significantly affect the assessments of the study safety outcomes.

The final list of protocol deviations will be reviewed, finalised and documented prior to database lock. Only important protocol deviations will be listed and tabulated in the Clinical Study Report (CSR). The following categories of protocol deviations will be reviewed by medical advisors and statisticians prior to database lock to determine those which are considered important deviations:

- Patients who do not meet the inclusion criteria
- Patients who meet any of the exclusion criteria
- Concomitant use of disallowed medications (to be identified through programming). Patients who use one or more disallowed medication (for any reason, unless otherwise specified) during the treatment period will be classed as protocol deviators
- Patients who received the incorrect study dose regimen
- Patients who developed withdrawal criteria during the study but were not withdrawn

Any patients with anomalies in the plasma concentrations, determined as follows, will be flagged and discussed in the CSR:

- Patients for whom all collected plasma concentration levels are persistently below the LLOQ (3.86 ng/ML) throughout the treatment period
- Patients with plasma concentrations in excess of what is considered to be physiologically possible with dosing (ie concentrations $\geq 12,000$ ng/ML)

A listing will be prepared for these patients highlighting the PK sampling times along with their results from the ADA and eosinophil assessments.

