2.5 Prior/Concomitant medications

Medication will be classified as a maintenance asthma medication at baseline if it started prior to or on the date of first dose of IP in BORA and was ongoing after the first dose of IP. Inhaled corticosteroid (ICS) doses will be converted to their Fluticasone Propionate dry powder equivalent in micrograms. Oral corticosteroid (OCS) doses will be converted to their Prednisolone equivalent in milligrams.

An asthma medication will be regarded as prior if it was stopped on or before the date of first dose for the study (medication stop date \leq date of the first dose).

Medication will be regarded as concomitant if the start date is after the date of first dose in BORA, or if it started prior to the date of first dose and was ongoing after the date of first dose. Medications with start date after the on-treatment period (as is defined for adverse events in Section 3.1.1) will not be considered as a concomitant.

Medications recorded in the predecessor studies that were ongoing or stopped after the first dose of BORA are integrated with BORA data for summaries.

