3.1.1 Adverse events

Adverse event (AE) and serious adverse event (SAE) are defined in Section 7.1 of the CSP. All AEs, including SAEs, will be collected from the time the patient signs the informed consent throughout the treatment period and including the follow-up period (Visit 16, Week 68 for adults, and Visit 29, Week 120 for adolescents). Any AEs that are unresolved at follow-up in the study will be followed up by the Investigator for as long as medically indicated, but without further recording in the CRF. If the record was entered in CRF for an ongoing event post-study follow-up visit, study output will list those events and indicates as such.

Adverse events experienced by the patients will be collected throughout the entire study and will be coded by the AstraZeneca designee using the latest version of the Medical Dictionary for Regulatory Activities (MedDRA).

Adverse event data will be categorised according to their onset date into the following study periods:

- AEs in the on-study period are defined as those with onset between the day of first dose of study treatment and the day of the scheduled follow-up visit, inclusive.
- AEs in the on-treatment period are defined as those with onset between the day of the first dose of study treatment and scheduled EOT for patients who complete study treatment or scheduled IPD visit for those patients who prematurely discontinue study treatment, inclusive. If the EOT or IPD visit is beyond the protocol defined visit window, AEs with onset after the day of last dose of study treatment date + 28 days + 7 days (visit window) will be excluded from the on-treatment period and instead assigned to the post-treatment period.
- AEs in the post-treatment period are defined as those with onset after an on-treatment period defined above.

For instances where a patient attends the safety follow-up visit only, but does not attend an earlier IPD visit or EOT visit, adverse events occurring on or after the day of the first dose of study treatment and on or before the last dose of study medication + 28 days will be assigned to the on-treatment period, while AEs with onset date after this time will be assigned to the post-treatment period.

For adolescent data included in the adult completion analyses, only on-treatment AEs will be summarised. AEs will be categorised as having occurred in the on-treatment period if they satisfy one of the following conditions.

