4.2.3 Concomitant medication

The number and percentage of patients who take concomitant medications, and those who take disallowed concomitant medications during the study, will be presented by treatment group. Concomitant medications will be classified according to the AstraZeneca Drug Dictionary (AZDRUG). The summary tables will present data by generic term within ATC code.

The number and percentage of patients taking maintenance asthma medications, including ICS/LABA fixed dose combinations, at baseline will be summarised and for those patients taking ICS and OCS at the study baseline, the converted dose will be summarised. The number of patients treated with ICS and OCS at baseline will be summarised separately by ATC code and preferred term, with total daily dose (non-converted) at baseline summarised for each preferred term. A similar summary will be prepared to summarise total daily dose of OCS at baseline. For patients from ZONDA, all OCS taken at baseline regardless of reason for therapy will be included to be consistent with the way the data was reported and analysed in ZONDA.

All above summaries also will be summarised for the patients who rolled over to MELTEMI study.

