4.2.6.1 Asthma exacerbation

Annual asthma exacerbation rate

The annual asthma exacerbation rate will be summarised descriptively by the treatment group. On-treatment exacerbation, post-treatment exacerbation, as well as on-study exacerbation rates will be summarised separately. All exacerbation incidences will be listed.

Time to the first asthma exacerbation

Time to the first asthma exacerbation will be described using a Kaplan-Meier plot by the treatment group. Note that this calculation will only be displayed for patients who received placebo in the predecessor studies.

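### Biologics and immunosuppressives started between end of treatment and follow-up reach no planned medication table and no disallowed-drug deviation check, although the protocol still bans them and the SAP reports post-treatment rates for that period

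*SAP*

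**What the plan says.** **Medication tables.** SAP 2.5 defines which drugs count as concomitant and closes with this limit: "Medications with start date after the on-treatment period (as is defined for adverse events in Section 3.1.1) will not be considered as a concomitant". SAP 4.2.3 then plans to tabulate "The number and percentage of patients who take concomitant medications, and those who take disallowed concomitant medications during the study". No other table of medications taken during BORA is described.

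**End of the on-treatment period.** Under SAP 3.1.1 the period runs through the EOT visit day, or the IPD visit day for patients who stop early, and includes that day. For late visits there is a cap: "AEs with onset after the day of last dose of study treatment date + 28 days + 7 days (visit window) will be excluded". Such events count as post-treatment.

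**Deviations.** SAP 2.2.1 gives the rule for banned drugs: "Patients who use one or more disallowed medication (for any reason, unless otherwise specified) during the treatment period will be classed as protocol deviators". A separate category in the same list reads "Patients who meet any of the exclusion criteria".

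**The bans.** Appendix F, Table 2, prohibits any marketed or investigational biologic before and during treatment and for "4 months or 5 half-lives (whichever is longer) after the last dose of the investigational product". Immunomodulators and immunosuppressives, apart from stated steroid exceptions, remain prohibited for the longer of 3 months and 5 half-lives after the last dose. Live vaccines remain prohibited for 16 weeks.

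**The rates.** SAP 4.2.6.1 states: "On-treatment exacerbation, post-treatment exacerbation, as well as on-study exacerbation rates will be summarised separately". SAP 3.4 does the same for healthcare encounters. The SAP amendment history gives the reason for a separate "post-treatment period to investigate whether the underlying exacerbation rate changes with withdrawal of treatment", with a parallel reason for healthcare encounters.

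**The concern.** The SAP describes what happens to exacerbations and healthcare use after benralizumab stops. That is also the one period whose newly started drugs are left out of the planned medication tables. If some patients start another biologic between EOT and follow-up, their events and person-time stay in the post-treatment rate, and no planned summary shows how many did so. An effective replacement would lower the rate and make stopping look more benign.

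The deviation rule has the same gap. A biologic started in those weeks breaches the protocol but does not meet the SAP's definition of a disallowed-medication deviation. SAP 2.2.1 (treatment period) and SAP 4.2.3 (whole study) also use different windows for the same class of drug. SAP 6 records no change from the protocol.

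**Working it through.** **Inputs.** Adults: last dose Week 52, EOT Week 56, follow-up Week 68 (protocol synopsis, duration of treatment). Adolescents: Weeks 104, 108 and 120. End of on-treatment: EOT day, or at most last dose + 28 + 7 = 35 days (SAP 3.1.1). Bans: Appendix F, Table 2.

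**Step 1: reproduce the plan's follow-up length.** 68 − 52 = 16 weeks, and 120 − 104 = 16 weeks. Both agree with the protocol. 16 × 7 = 112 days.

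**Step 2: days after the on-treatment period, on the nominal schedule.**
- EOT on time: 112 − 28 = 84 days; 84/112 = 75%.
- At the cap: 112 − 35 = 77 days; 77/112 = 69%.

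**Step 3: share of each ban that falls after on-treatment and before follow-up.** Months are converted at about 30.4 days.

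| Class | Post-dose ban (stated minimum) | Days outside the window | Share |
|---|---|---|---|
| Biologics | 4 months, about 122 days | 77 to 84 | 63 to 69% |
| Immunosuppressives | 3 months, about 91 days | 56 to 63 | 62 to 69% |
| Live vaccines | 112 days | 77 to 84 | 69 to 75% |

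The biologic ban also runs about 122 − 112 = 10 days past the nominal follow-up visit, so every biologic started before that visit is a breach. If the 5-half-life term governs immunosuppressives and equals 16 weeks, as the protocol equates the two for benralizumab, their share becomes 69 to 75%.

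**Step 4: follow one case through the rules.** A patient completes EOT at Week 56 and starts a biologic at Week 58.
- Recorded? Yes. Protocol 3.5.1 collects treatments at each visit, and Table 1 marks concomitant medication through follow-up.
- Concomitant under SAP 2.5? No: it started after the on-treatment period.
- In the SAP 4.2.3 tables? No: they cover concomitant drugs only.
- Disallowed-medication deviation under SAP 2.2.1? No: the use falls outside the treatment period.
- In the post-treatment rates? Yes. SAP 4.1 keeps all data whether or not the patient adhered to the protocol, and no rule flags or censors replacement therapy.

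**Step 5: illustration on assumed values.** Let f be the share of post-treatment person-time on a replacement drug and RR its rate ratio against none. Then observed rate / untreated rate = 1 − f(1 − RR). Neither f nor RR is in the documents.
- f = 5%, RR = 0.7: 1 − 0.05 × 0.3 = 0.985.
- f = 20%, RR = 0.5: 1 − 0.20 × 0.5 = 0.90.

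Over that assumed range, the understatement is 1.5% to 10%.

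**The case against.** Several points on the other side stand and limit the concern.

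- **Switches on the EOT day are caught.** The on-treatment period includes that day, as does the treatment period in protocol 8.4.1. Only later starts are missed.
- **Live vaccines arguably have another route.** Exclusion criterion 5 runs to 16 weeks after the last dose, and meeting an exclusion criterion is a reviewed category with no treatment-period limit. No equivalent post-dose criterion exists for biologics or immunosuppressives.
- **The drugs are not hidden.** A reader might infer that they vanish from the record. They are collected, and SAP 4.1.1 runs adult listings to follow-up. However, no medication listing is named, and a listing would not summarise use by group. SAP 2.3 promises that all data are listed or analysed, but with an exception for anything specified otherwise, which SAP 2.5 does for the tables.
- **Including later therapy can be deliberate.** SAP 4.1 takes a treatment-policy approach, and the withdrawal purpose appears only in the amendment history. The operative sections define three descriptive rates and no formal contrast. This defends the rate itself, but leaves readers without the medication use they need to interpret it.
- **The scope is narrow.** Patients who move to MELTEMI leave BORA at transition, and adolescents contribute only on-treatment data to the adult completion analysis. Early discontinuers do contribute, because protocol 3.6 asks them for an IPD visit and a follow-up visit 16 weeks after the last dose.

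**Conclusion.** The gap is real for biologics and immunosuppressives started after EOT or IPD and before follow-up: about 77 to 84 of the 112 post-dose days for an adult completer on the nominal schedule. Such starts appear in no planned summary table and are not classed as disallowed-medication deviations, although the protocol still prohibits them for all or most of that time and the data are collected.

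A reader might go further and infer that the post-treatment exacerbation rate is biased and that stopping benralizumab will look safer than it is. The documents do not support that. They give no share of patients starting another drug and no effect size, and every biologic start before follow-up would be a breach, so use may be rare. Only the direction can be stated: if an effective replacement is used, the post-treatment rate, and the post-treatment part of the on-study rate, would be lower than without it. The consequence is for interpretation of descriptive secondary endpoints in a study with no planned hypothesis tests. The correction should be made because it is cheap and because, without it, the SAP does not check bans that the protocol imposes.

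**What to change.** 1. In SAP 2.2.1, replace the treatment-period limit on disallowed medication with the period in which Appendix F prohibits the drug, up to the follow-up visit. Reconcile the whole-study wording in SAP 4.2.3 with it.
2. Keep the on-treatment concomitant table. Add one table by treatment group of medications started post-treatment through follow-up: biologics, immunosuppressives, maintenance OCS and other asthma controllers.
3. Optional, as a supportive display only: repeat the post-treatment exacerbation and healthcare-encounter rates with events and person-time stopped at the first prohibited biologic. State that this censoring may be informative, since patients who start one may be those who are worsening.

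The cost of items 1 and 2 is SAP wording and one extra table on data already scheduled for collection, with slightly more deviators reported. Item 3 would add a repeat of two rate tables.

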3. PRIMARY AND SECONDARY VARIABLES

3.1 Safety outcome variables

The following safety data will be collected: reported AEs, clinical chemistry, haematology, urinalysis, local 12-lead ECG, vital signs, and physical examination. There will be no imputation for missing values for all the safety variables.

Change from baseline to each post-treatment time point where scheduled assessments are performed will be calculated for relevant measurements.

3.1.1 Adverse events

Adverse event (AE) and serious adverse event (SAE) are defined in Section 7.1 of the CSP. All AEs, including SAEs, will be collected from the time the patient signs the informed consent throughout the treatment period and including the follow-up period (Visit 16, Week 68 for adults, and Visit 29, Week 120 for adolescents). Any AEs that are unresolved at follow-up in the study will be followed up by the Investigator for as long as medically indicated, but without further recording in the CRF. If the record was entered in CRF for an ongoing event post-study follow-up visit, study output will list those events and indicates as such.

Adverse events experienced by the patients will be collected throughout the entire study and will be coded by the AstraZeneca designee using the latest version of the Medical Dictionary for Regulatory Activities (MedDRA).

Adverse event data will be categorised according to their onset date into the following study periods:

- AEs in the on-study period are defined as those with onset between the day of first dose of study treatment and the day of the scheduled follow-up visit, inclusive.
- AEs in the on-treatment period are defined as those with onset between the day of the first dose of study treatment and scheduled EOT for patients who complete study treatment or scheduled IPD visit for those patients who prematurely discontinue study treatment, inclusive. If the EOT or IPD visit is beyond the protocol defined visit window, AEs with onset after the day of last dose of study treatment date + 28 days + 7 days (visit window) will be excluded from the on-treatment period and instead assigned to the post-treatment period.
- AEs in the post-treatment period are defined as those with onset after an on-treatment period defined above.

For instances where a patient attends the safety follow-up visit only, but does not attend an earlier IPD visit or EOT visit, adverse events occurring on or after the day of the first dose of study treatment and on or before the last dose of study medication + 28 days will be assigned to the on-treatment period, while AEs with onset date after this time will be assigned to the post-treatment period.

For adolescent data included in the adult completion analyses, only on-treatment AEs will be summarised. AEs will be categorised as having occurred in the on-treatment period if they satisfy one of the following conditions.

For adult completion analysis, the last dose date for an adolescent is defined as the date of last administered dose on or prior to Week 56.

- For patients who received study treatment at Week 56, AEs in the on-treatment period are defined as those with onset between the date of the first BORA study treatment and the Week 56 visit, inclusively.
- For patients who missed Week 56 visit but continued study after Week 56, AEs with onset on or prior to the last dose date of study treatment (as defined above) + 28 days will be assigned to the on-treatment period.
- For patients who discontinued study treatment prior to Week 56 and had IPD visit, AEs with onset on or prior to the IPD visit date or the last dose date (as defined above) + 28 days + 7 days, whichever is earlier, will be included in the on-treatment period.
- For patients who discontinued study treatment prior to Week 56 and had no IPD visit, AEs with onset on or prior to the date of the last dose of study treatment (as defined above) + 28 days will be assigned to the on-treatment period.

If an AE has a missing onset date then unless the stop date of the AE indicates otherwise, this will be considered an on-treatment event. If an AE has a partial onset date, the handling of partial/missing dates is detailed in Section 8.2.

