3.7 Withdrawal from the study

3.7.1 Withdrawal of Informed Consent

Patients are free to withdraw from the study at any time (IP and assessments) without prejudice to further treatment. Patients who discontinue IP will be discontinued from the study.

A patient who withdraws consent will always be asked about the reason(s) and the presence of any adverse events (AE). The Investigator will follow up AEs outside of the clinical study. The enrolment/randomization code of the withdrawn patient cannot be reused.

If patient agrees, he/she will be asked to return to the study center and complete procedures described for the IPD and FU visits within 4 weeks (+7 days) and 16 weeks (\pm 7 days) after the last dose of IP, respectively.

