3.2.1.2 Time to first asthma exacerbation

Time to first asthma exacerbation will only be calculated for the patients who were randomised to placebo in the predecessor studies with start of exacerbation during the on-treatment period, and is calculated as follows:

$$\text{Start Date of first asthma exacerbation} - \text{date of first dose} + 1.$$

The time to first asthma exacerbation for patients who do not experience an asthma exacerbation during the treatment period will be censored at their end of on-treatment period as defined in AE Section of 3.1.1.

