4.2.10 Analysis method for immunogenicity variables

Demographic and patient characteristics including age, sex, race, ethnicity group and BMI subgroups ($\leq 35 \text{ kg/m}^2$, $> 35 \text{ kg/m}^2$) by ADA status (positive, negative) and ADA positive subgroups (stable persistently positive, nAb positive) will be presented by treatment group.

The number and percentage of patients within each ADA response category defined in Section 3.6 will be summarised by treatment group and ADA status in predecessor studies. Anti-drug antibody response and the corresponding titre will be summarised by visits. In addition, the ADA response will be presented cumulatively by visit. A summary of ADA titres over time by ADA status (ADA positive patients at any visit, ADA newly persistently positive, ADA stable persistent positive, and nAb positive patients) will be provided to monitor titre changes over time.

Newly persistently positive ADA response and ADA stable persistently positive by maximum titer quartile subgroups will be presented by treatment group. A table will be presented to list patients in each treatment group with treatment boosted ADA, and repeated for those patients with maximum titer above the 3rd quartile. For each patient, the table will list the titre at study baseline, maximum titre, and the fold-change that is above the 3rd quartile of the maximum titre from baseline. Similar summaries will be provided for patients with decrease in titre

including the baseline titre, maximum titre, post maximum titre that is decreased >75% from the maximum titre, and its percent reduction from the maximum titre.

The relationship among the following parameters with ADA status (positive, negative) and ADA positive subgroups (ADA titre greater than median of the maximum, newly persistently positive, stable persistently positive, nAb positive) will be presented, unless stated otherwise.

- The annual exacerbation rate during on-study period, on-treatment period and post-treatment period
- Change from baseline in pre-BD FEV₁ for each post-baseline visit
- Adverse events (AEs) and serious adverse events (SAEs) by System Organ Class (SOC) and Preferred Term (PT), AEs and SAEs by preferred term, AEs and SAEs by PT and causality, and hypersensitivity events by PT and causality. These summaries will be conducted during on-treatment period. Additional AE summaries may be added as needed, based on review of the pre-specified summaries

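### SAP 3.1.1 ends on-treatment time at the IPD visit with a late cap but no minimum, so an early attender can get a shorter on-treatment period than a patient who skips the visit

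*SAP*

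**What the plan says.** **Adults, general rule (SAP 3.1.1).** On-treatment AEs are those with onset from first dose to "scheduled EOT for patients who complete study treatment or scheduled IPD visit for those patients who prematurely discontinue study treatment, inclusive". The next sentence deals only with late visits. It opens "If the EOT or IPD visit is beyond the protocol defined visit window" and provides that AEs starting after "last dose of study treatment date + 28 days + 7 days (visit window) will be excluded from the on-treatment period".

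**Adults, no IPD or EOT visit but follow-up attended (SAP 3.1.1).** AEs with onset "on or before the last dose of study medication + 28 days will be assigned to the on-treatment period".

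**Adolescents in the adult completion analysis (SAP 3.1.1).** For those who stop before Week 56 and have an IPD visit, the period ends at "the IPD visit date or the last dose date (as defined above) + 28 days + 7 days, whichever is earlier". For those with no IPD visit, it ends at last dose + 28 days.

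**Where the same end date is used.** SAP 3.2.1.1 applies the AE periods to exacerbations and to their follow-up time. In SAP 3.2.1.2, patients without an exacerbation "will be censored at their end of on-treatment period as defined in AE Section of 3.1.1". SAP 4.2.5.1 uses the periods for AE person-time. For AEs, SAEs and hypersensitivity events by ADA status, SAP 4.2.10 says "These summaries will be conducted during on-treatment period". SAP 3.1.1 and 4.1.1 restrict adolescent AE summaries in the adult completion analysis to the on-treatment period.

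**When the IPD visit happens (Protocol).** Sections 3.6 and 4.2.3.4 place it within 4 weeks, with a tolerance of ± 7 days, after the last dose. Section 3.7.1 asks patients who withdraw to "complete procedures described for the IPD and FU visits within 4 weeks (+7 days" after the last dose. The footnotes to Tables 1, 2A and 2B also give + 7 days only, and count from the last scheduled site visit.

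**The concern.** The length of a premature stopper's on-treatment period depends on whether and when the patient attends the IPD visit. Prompt attendance shortens the period and non-attendance gives the full 28 days, although both patients may have had the same last dose and the same later event.

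The 28-day tail is the SAP's own yardstick. It separates the last dose from EOT for completers, and it is the rule for patients with no IPD visit and for adolescents who miss Week 56 but continue. Only the early IPD visit falls short of it.

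Three outputs have no on-study counterpart that would still show a reclassified event:

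- AE, SAE and hypersensitivity tables by ADA status. Protocol 1.4 names hypersensitivity as a theoretical ADA risk.
- Adolescent AE tables in the adult completion report, until the addendum.
- The Kaplan-Meier plot for former placebo patients. A patient who stops and is seen early is censored at that visit even if an exacerbation is recorded shortly afterwards.

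**Working it through.** **1. Reproduce the plan's 28 and 35 days.** From SAP Appendix A, Table 2:

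- Adults: last dose (Week 52) on study day 365 and EOT on day 393, so 393 − 365 = 28.
- Adolescents: last dose (Week 104) on day 729 and EOT on day 757, so 757 − 729 = 28.
- Adding the 7-day window gives 28 + 7 = 35, which is the stated cap.

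**2. On-treatment tail after the last dose.** For an IPD visit *d* days after the last dose, taking the actual visit date as the cut, tail = min(*d*, 35). With no IPD visit, tail = 28. The last column applies the rule proposed below, min(max(*d*, 28), 35).

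| IPD visit, days after last dose | Tail now | Difference from no visit | Tail under proposed rule |
|---|---|---|---|
| 3 | 3 | −25 | 28 |
| 7 | 7 | −21 | 28 |
| 14 | 14 | −14 | 28 |
| 21 | 21 | −7 | 28 |
| 28 | 28 | 0 | 28 |
| 35 or later | 35 | +7 | 35 |
| no visit | 28 | 0 | 28 |

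**3. What the protocol windows imply.**

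- Read as 28 ± 7 days (Sections 3.6 and 4.2.3.4), a compliant visit falls on days 21–35. The largest loss is 28 − 21 = 7 days.
- Read as any time up to 4 weeks, plus 7 days (Section 3.7.1 and the table footnotes), there is no lower limit. The loss can approach 28 days.

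**4. Study-level size.** The documents do not give the number or timing of early IPD visits. Assumptions: 1200 patients; a fraction *p* of 5–15% stops early, at about mid-treatment (day 196); every stopper has the IPD visit on the same day *d*, from 7 to 21; completers contribute 392 days.

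Time moved = 1200 × *p* × (28 − *d*) / 365.25 patient-years.

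On-treatment time = [1200 × (1 − *p*) × 392 + 1200 × *p* × (196 + *d*)] / 365.25 patient-years.

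- Low end (*p* = 5%, *d* = 21): 1200 × 0.05 × 7 / 365.25 = 1.15, out of 1259.1 (0.09%).
- High end (*p* = 15%, *d* = 7): 1200 × 0.15 × 21 / 365.25 = 10.35, out of 1194.7 (0.87%).

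At an assumed 1 event per patient-year this is about 1 to 10 events. Across assumed rates of 0.5 to 3 per patient-year it is about 0.6 (1.15 × 0.5) to 31 (10.35 × 3).

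**5. Which events move.** SAP 3.1.1 classifies by onset date. An event moves only if it starts after the IPD visit and no later than 28 days after the last dose. One that started before the visit, including the AE that led to stopping, normally stays on-treatment.

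**The case against.** **The word *scheduled* may mean a nominal date.** If it meant last dose + 28 days for adults, there would be no gap. This cannot be ruled out. However, the following sentence tests the visit against its window, and the adolescent rule names the visit date, so the actual date is the more natural reading. The two readings would be programmed differently, so the text needs settling either way.

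**The primary safety result does not depend on this.** That stands. A reader might infer that events vanish from the primary analysis. The primary objective covers treatment and the 16-week follow-up, and SAP 4.2.5.1 reports AEs on-study as well as by period. Adult on-study totals are unaffected. Adolescent events remain in the listings, and the addendum takes in all adolescent data to follow-up.

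**Rates lose time as well as events.** That also stands. Exacerbation follow-up and AE person-time are cut at the same date, so rates shift only if risk after the visit differs from risk before it. The documents do not show that it does. Exacerbation rates by ADA status are reported for all three periods.

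**Early visits may be out of window.** On the 28 ± 7 day reading, any loss above 7 days needs a non-compliant visit. The other protocol wording sets no lower limit, so both readings remain open.

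**Residual drug does not settle the tail.** It is tempting to argue that early attenders are still near full exposure. For blinded Q8W patients the last injection may have been placebo, so that argument fails for part of the study. The case here rests on consistency with the SAP's own 28 days.

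**Conclusion.** The inconsistency is real: explicit for adolescents in the adult completion analysis, probable for adults. It shifts new events that start after an early IPD visit into the post-treatment period. The practical effect is on counts and percentages in the on-treatment-only tables and on early censoring in the Kaplan-Meier plot.

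The overall effect is likely small: about 0.1–0.9% of on-treatment time under the assumptions above, with the true number of early visits unknown. A few events could be visible in the smaller ADA-positive and adolescent tables. The documents do not support reading this as a bias in the primary safety results or in the exacerbation rates. It is still worth correcting because the rule is internally inconsistent and the correction is almost free.

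**What to change.** **SAP 3.1.1, general rule and the adolescent rule for IPD attenders.** For premature stoppers, end the on-treatment period at the later of the actual IPD visit date and last dose + 28 days, capped at last dose + 35 days and at death or last contact. Where no IPD visit took place, use last dose + 28 days with the same limits. This also covers adults who attend neither the IPD nor the follow-up visit, for whom no rule is stated. Replace *scheduled* with the actual visit date. Sections 3.2.1.1, 3.2.1.2, 3.4, 4.2.5.1 and 4.2.10 then inherit the rule.

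**Alternative.** The proposed rule leaves up to 7 days between a late attender and a non-attender. A flat last dose + 28 days for all premature stoppers would remove that difference, at the price of 7 days for patients seen on day 35 or later.

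**Protocol.** Reconcile Sections 3.6, 3.7.1 and 4.2.3.4 with the table footnotes on the timing of the IPD visit, both the tolerance and the date from which it is counted.

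**Cost.** A short SAP edit and one derived date. No new data are needed, because AEs are collected to the follow-up visit. A few events will move from post-treatment to on-treatment, so on-treatment counts will look slightly less favourable.
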